## **10.12 Randomization**

Randomization will be performed at the baseline visit. If the patient participates in the biobank the randomization will be performed after collection of samples. Only patients with a high-risk pattern in the proteomic analysis from the screening visit will be randomized. Patients will be randomized in a 1:1 ratio to either active medication or placebo in addition to standard treatment as described in section 8. Patients will be stratified in the two treatment arms (1:1) based on whether or not the patients is treated with RAS blocking agents at the time of entry (Screening).

## **10.13 Adverse Events**

Documentation of all adverse events will be performed at all visits as indicated in table 1 and as described in section 13.1.

## **10.14 Significant medical event**

Documentation of significant medical events will be conducted at the annual visit for the low-risk participants. Any medical untoward occurrence after baseline can be documented as a significant medical event. Of special interest are events described in section 5.5.1 as secondary end points.

## **10.15 Urine dipstick test**

Urine dipstick test are to be performed on urine samples at the study sites to confirm that urine tract infection is present. Urine dipstick test is performed before the samples are frozen.

If the patients has a urinary tract infection or menstrual bleeding at the time of a planned study visit, urine collection should be postponed and the visit can be rescheduled, preferably within two weeks of the planned visit, or as soon as possible thereafter.

## **10.16 Pregnancy test**

All female patients with child-bearing potential will have a pregnancy test performed at the Screening visit, and at the end of study or discontinuation, as indicated in Table 1. The assessment will be according to local standard based on blood or urine analysis.

## **10.17 Final assessment**

At the Final assessment standard diabetic care according to local guidelines will be performed, as well as the study procedures indicated in table 1.

## **10.18 Clinical procedure after end of the study/ Early termination**

After the end of the study or early termination, the patients will receive standard care according to national guidelines under the discretion of the treating physician.

## **10.19 Unscheduled visit**

Unscheduled visit is possible any time after screening on the opinion of the investigator. The content of such visit is on the discretion of the investigator. The main issue for the unscheduled visit must be documented in the eCRF.

## 11 INVESTIGAL MEDICAL PRODUCTS

### 11.1 IMPS

All IMPs will be manufactured in accordance with EU Good Manufacturing Practice requirements and will be supplied and distributed by Mawdsleys Clinical Services UK.

Tablets and bottles containing active IMP or placebo will be indistinguishable from each other in terms of taste, appearance, durability, packaging, labeling and instruction for use.

Only patients of the intervention group will receive IMP. Only those supplies intended for use in the study may be dispensed to study participants.

#### 11.1.1 Formulation and preparation

Spironolactone: Tablet for oral use containing spironolactone and additional excipients

Placebo: matched placebo tablet for oral use. (Placebo tablets have the same constituents as the active with the exception of spironolactone content.)

#### 11.1.2 Administration

Patients will be advised to take the IMP tablets once each day orally, with or just after food in the morning.

Dosage Treatment: 25 mg spironolactone once daily.

Dosage titration is prohibited.

#### 11.1.3 Packaging

Packages with active or place study drug will be indistinguishable from each other.

Primary packaging will contain IMP for 13 weeks of treatment plus a small overage (110 tablets).

#### 11.1.4 Labeling

Labeling will be performed according to national regulatory requirements and in accordance with current annex 13 EU Good Manufacturing Practice requirements.

#### 11.1.5 Storage and stability

The IMPs will be provided to each participating study center from the study manufacturer in a blinded fashion.

The tablets should be stored in a dry place at room temperature below 25 °C in a secure location.

Study supplies must be stored under the correct storage conditions at all times.

### 11.2 Accountability procedures for the IMP

After randomization, patients of the intervention group will receive IMP from the study site they attend.

At every 13th week after the Baseline the patients should be asked to return the IMP for accountability.

Patient should take between 80-110% of IMP to be compliant. The process for capturing the compliance information is the assessment by tablet counts at each site.

A record of all IMP movements including drug dispenses must be performed and documented by each site.

### 11.3 Main side effects of spironolactone

Gynecomastia may develop in association with the use of spironolactone. Development appears to be related to both dosage level and duration of therapy and is normally reversible when the drug is discontinued. In rare instances some breast enlargement may persist.

The following adverse events have been reported in association with spironolactone therapy:

Organ system	Side effect
General disorders and administration site conditions	malaise
Neoplasms benign, malignant and unspecified (including cysts and polyps)	benign breast neoplasm
Gastrointestinal disorders	gastrointestinal disturbances, nausea
Blood and lymphatic system disorders	leukopenia (including agranulocytosis), thrombocytopenia
Hepatobiliary disorders	hepatic function abnormal
Metabolism and nutrition disorders	electrolyte disturbances, hyperkalemia
Musculoskeletal disorders	leg cramps
Nervous system disorders	dizziness
Psychiatric disorders	changes in libido, confusion
Reproductive system and breast disorders	menstrual disorders, breast pain
Skin and subcutaneous tissue disorders	Stevens-Johnson syndrome (SJS), toxic epidermal necrolysis (TEN), drug rash with eosinophilia and systemic symptoms (DRESS), alopecia, hypertrichosis, pruritus, rash, urticaria
Renal and urinary disorders	acute renal failure

### 11.4 Overdose

Acute overdosage may be manifested by drowsiness, mental confusion, nausea, vomiting, dizziness or diarrhoea. Hyponatremia, or hyperkalemia may be induced, but these effects are unlikely to be associated with acute overdosage. Symptoms of hyperkalemia may manifest as paresthesia, weakness, flaccid paralysis or muscle spasm and may be difficult to distinguish clinically from hypokalemia. Electrocardiographic changes are the earliest specific signs of potassium disturbances. No specific antidote has been identified. Improvement may be expected after withdrawal of the drug. General supportive measures including replacement of fluids and electrolytes may be indicated. For hyperkalemia, specific procedures are to be followed as described in the Appendix.

### **11.5 Risks in connection with the investigation procedures**

The collection of the urine samples is without. The blood withdrawals for research purposes will be performed in relation to standard investigational procedures. As with any venepuncture, pain, bleeding and/or bruising may occur due to penetration of the needle; more rarely, infection can occur at the entry spot. Very rarely, there may be arterial puncture, nerve damage or phlebitis.

## 12 CONMEDICATION AND TREATMENT

### 12.1 Treatment in general

Treatment of any medical condition aside from hypertension, albuminuria and hyperkalemia must be in accordance with local guidelines. Treatment of hypertension, albuminuria and hyperkalemia should be carried out in accordance with the study protocol, section 12.2, 12.3 or 24.

All participants in the trial can receive anti-diabetic treatment in accordance with local guidelines and standard of care. The treatment regimen can include dietary advice, oral- and/or injection of anti-diabetic medication.

### 12.2 Prohibited medication

Participants are prohibited to use the following medical treatment in the duration of the study:

ATC-code	Drug class	Drug example
C03D	Potassium-sparing diuretics	Spironolactone, Eplerenone, Amilorid
C03E	Diuretics and potassium-sparing agents in combination	C03D in combination with other drugs
N05AN	Lithium salt	Lithium

### 12.3 Hypertension treatment

It can be expected that the included study population will be heterogeneous at baseline in terms of antihypertensive treatment, as this may reflect different individual and local treatment considerations. Antihypertensive treatment prior to inclusion, especially ACE or ARB treatment, should be continued unchanged during “run-in” period and throughout the study if possible.

**Definition:** Hypertension, for the purpose of this study, is defined as systolic pressure >130 mm HG and/or diastolic pressure >80 mm Hg.

All patients should be treated according to local guidelines. In any case the care team should be encouraged to initiate or intensify treatment in case of repeated (or confirmed) blood pressure > 140 mm Hg systolic and or diastolic > 90 mmHg. If local guidelines do not recommend a specific first line antihypertensive agent it is suggested to start with a calcium channel blocker or thiazide diuretic to reduce interference with UACR.

In any case, choice of therapy is left to the discretion of the investigator. RAS blocking agents are accepted, if indicated. If blood pressure cannot be managed consideration of a secondary cause should be studied. If patients are assigned to IMP is started on ACE, ARB or renin-inhibitors the investigator is advised to measure potassium according to local guidelines, to minimize the risk of hyperkalemia.

### 12.4 Albuminuria treatment

All participants included in the trial are normoalbuminuric (UACR <30 mg/g). If a participant reaches the primary endpoint during the course of the study, the information will be flagged in the eCRF and the investigator will be notified.

Participants not in treatment with ACE or ARB at the time of screening should not start treatment before the primary endpoint is reached.

## 13 ADVERSE EVENT MONITORING AND REPORTING

### 13.1 Definitions

#### 13.1.1 Adverse Events

An AE as defined in this study is any untoward medical occurrence in a patient or clinical trial patient after baseline. The event does not necessarily have to have a causal relationship with that treatment. AEs can be diseases, signs of disease or symptoms. Among others, AEs include the following:

- All suspected medication adverse reactions
- Apparently unrelated illnesses, including the worsening of a preexisting illness, injury or accidents
- Laboratory abnormalities that require clinical intervention
- Accidents and complications from diagnostic interventions

The following events do not fulfil the definition of an AE:

- An elective hospitalization during participation in a trial for an intervention or diagnostic procedure for a condition which was present before entering the trial
- A pre-existing disease or condition which does not deteriorate during the participation in the trial

#### 13.1.2 Adverse Reaction

An AR is any untoward and unintended response to the IMP related to any dose administered. A response to the medicinal product is given when a causal relationship between the adverse event and one of the IMPs is at least a reasonable possibility.

#### 13.1.3 Serious Adverse Events/ Reaction

A SAE or SAR is any untoward medical occurrence that at any dose:

- Results in death
- Is life-threatening  
(i.e., in the opinion of the investigator, the patient is at immediate risk of death from the event)
- Requires in-patient hospitalization or prolongation of existing hospitalization.
- Results in persistent or significant disability/incapacity  
(i.e. a substantial disruption of a person's ability to conduct normal life functions)
- Is a congenital anomaly/birth defect

Important AEs that may not result in death, may not be life-threatening, or do not require hospitalization may be considered serious when, based upon appropriate medical judgment, they may jeopardize the patient and may require medical or surgical intervention to prevent one of the outcomes listed above.

The following events do not fulfill the definition of an SAE:

- Events which might have resulted in a life-threatening situation but did not

- Elective hospitalization during participation in a trial for an intervention or diagnostic procedure for a condition which was present before entering the trial

### **13.1.4 Suspected Unexpected Serious Adverse Reaction**

A SAE, the nature or severity of which is not consistent with the applicable product information.

## **13.2 Reference document / Applicable product information**

The applicable product information for this trial is the summary of medicinal product characteristics from [http://www.medicines.org.uk/emc/medicine/9136/SPC/of\\_13/12/2012](http://www.medicines.org.uk/emc/medicine/9136/SPC/of_13/12/2012) respectively its updates (actual version - [http://www.medicines.org.uk/emc/medicine/9136/SOC/of\\_03/03/2015](http://www.medicines.org.uk/emc/medicine/9136/SOC/of_03/03/2015)).

## **13.3 Documentation and reporting of AE**

### **13.3.1 Documentation requirements**

#### **13.3.1.1 AEs**

AE will be collected by the investigator either based on the information provided spontaneously by the patient or evaluated by non-suggestive questions.

The following information is necessary:

- Type of AE (disease, symptoms)
- Classification (serious vs. nonserious)
- Start and termination date of the AE
- Grading of AE-intensity (grade 1-5). The descriptions and grading scales found in the revised NCI CTCAE version 4.0 will be used for adverse event reporting.
- Causality to the study drug
- Measures taken with regard to study medication and treatment of the AE
- Outcome of the AE

The AE documentation period for this trial begins upon first administration of the IMP. In case of continuation of any AE the documentation period will be prolonged until all AEs are resolved or until the investigator assesses the adverse events as "chronic" or "stable".

Site investigator is responsible for monitoring the safety of patients enrolled into the study at the study sites. All AEs will be documented in the patient's medical record and managed according to standard practice.

The following AEs will additionally be documented in the eCRF:

- AEs leading to study drug discontinuation and/or withdrawal
- Serious AEs (SAEs, see Section 13.1.3)
- AEs related to cardiovascular and/or renal disease
- AEs related to retinopathy (and corresponding laser treatment)

- Laboratory abnormalities suspected by the investigators to be related to the study drug including the potassium and sodium value

At each patient visit the investigator will review the patient's medical record and determine if there have been any serious adverse events (SAEs) and/or AEs to be documented.

All eCRF-documented AEs, SAEs and laboratory abnormalities must be graded for severity and relationship to study drug and will be coded using the MedDRA via MARVIN.

Documentation of AEs must be performed in a timely manner on the respective AE forms in the eCRF.

### **13.3.1.2 SAEs**

The same documentation responsibilities as described for AEs apply to SAEs as well. In addition, SAEs must be documented on the paper SAE-form and reported to the sponsor. Documentation of SAE must be as complete and detailed as possible. In case of death, an autopsy should be aimed for and the results should be forwarded to the principal investigator and the sponsor.

## **13.3.2 Reporting requirements**

### **13.3.2.1 Reporting period**

The reporting period for AEs and SAEs begins with the first application and ends 30 days after the last application of the IMP.

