#### **14.6 Criteria for discontinuation**

A participant must be discontinued in the IMP treatment if any of the following is present:

- Female patients in the intervention study who become pregnant, intend to become pregnant or do not use adequate birth control (according to inclusion criteria 7, in section 7.1).
- Experience of research-related injury or unacceptable side effects to the study medication.
- Safety considerations assessed by the investigator
- Treatment with Lithium (ATC: N05AN).
- Treatment with potassium sparing diuretics (ATC: C03D, C03E).
- Confirmed eGFR below 15 ml/min/1.73 m^2.
- Confirmed elevated liver enzyme (ASAT and/or ALT) 3 times above normal range.

Discontinued patients will be offered tests corresponding to the final study visit. Data on all patients will be included in the study and will be used in safety analysis.

After discontinuation of study medication in the randomized population, observation should continue with visits as planned in the observational group (if the patient accepts), or if that is not possible/acceptable, evaluation of vital status and development of endpoints should be evaluated through registries, information of hospitals and GPs, or interviews with the patient as appropriate and possible in order to monitor development of endpoints in all included patients as thoroughly as possible, provided that the patient agrees.

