### **24.5 Continuation of study medication**

If the potassium level is  $< 0.9$  mmol/L above upper reference range the patient can continue taking study medication.

Patients who continue study medication after temporary discontinuation of study medication must have the potassium measured according to section 24.2.5

In a patient who has experienced a potassium level of  $\geq 1.4$  mmol/L above upper reference range, and in whom the potassium fails to decrease to  $< 0.9$  mmol/L above upper reference range after the procedures described above have been tried, the study medication must be discontinued permanently and it should be recorded in the eCRF.

In case of repeated episodes of confirmed hyperkalemia after the attempt to re-start study medication following discontinuation the study medication must be discontinued permanently and it should be recorded in the eCRF.

Patients, who discontinue the study medication, will remain in the study and be followed for the full duration of the study.

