5.4 Withdrawal/ follow-up

Time of follow-up will be estimate from baseline to end – exposure time measure in day/years. Participants who withdraw will be included in the analysis with exposure time from baseline to last observation. Participants who withdraw consent are included in the statistical analysis unless they specifically also withdrawal consent to use of data already entered in the eCRF.

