6.1.2 Secondary outcome

- A. Comparison of composite fatal and non-fatal cardiovascular outcome (MI, stroke, CABG, PTCA, hospitalization for heart failure and CVD) and all-cause mortality during the study.
- B. Comparison of incidence of retinopathy and frequency of laser treatment. Data collected from self-reported AEs.
- C. In addition to the categorical analysis of UACR, an analysis will be performed with changes in geometric mean of UACR throughout the study period in all patients by assessing the slope of albuminuria changes and absolute changes from inclusion to end of trial.
- D. Development of microalbuminuria (UACR >30 mg/g) in at least one morning void urine sample will be used as a secondary outcome instead of confirmed microalbuminuria.
- E. Development of macroalbuminuria (UACR >300 mg/g) in 2 out 3 first morning void urine samples).
- F. For patients with eGFR ≥ 60 ml/ min/ 1.73 m² at baseline, development of eGFR <60 ml/min/1.73m².
- G. Development of CKD stage 4 (eGFR <30 ml/min/1.73m²).
- H. Change in eGFR (slope) from baseline and from three-month post-baseline to end of study.
- I. Change in eGFR (40 % reduction) from baseline and from three-month post-baseline to end of study.
- J. Safety: Adverse Events and Serious Adverse Events. Adverse Events leading to death or discontinuation of study medication and/or withdrawal.
- K. Event of hyperkalaemia with potassium level in plasma ≥ 5.5 mmol and/or ≥ 5.8 mmol in serum at any time point.

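### Off-drug retinopathy, laser and non-fatal cardiovascular events in the high-risk group have no assured place in secondary outcomes B and A, although that time is counted as at risk

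*Protocol*

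**What the plan says.** **Safety window.** Protocol 13.3.2.1, under the reporting requirements, states: "The reporting period for AEs and SAEs begins with the first application and ends 30 days after the last application of the IMP". Documentation is covered separately in 13.3.1.1: "The AE documentation period for this trial begins upon first administration of the IMP". That section extends the period for AEs still running but gives no stop date. The AEs it sends to the eCRF include "AEs related to cardiovascular and/or renal disease" and retinopathy with its laser treatment.

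**Follow-up after stopping study drug.** Protocol 24.5: "Patients, who discontinue the study medication, will remain in the study and be followed for the full duration of the study". Protocol 14.6 says that "observation should continue with visits as planned in the observational group"; where that is not possible or acceptable, endpoints and vital status are to be sought from registers, hospital or GP information, or interviews. SAP 5.4: "Time of follow-up will be estimate from baseline to end". Only patients who withdraw are cut at their last observation, and SAP 6.2 rules out censoring.

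**Endpoint source.** SAP 6.1.2 B: "Comparison of incidence of retinopathy and frequency of laser treatment. Data collected from self-reported AEs". Protocol 5.5.2 also names AEs as the source for this outcome in the high-risk group. SAP 6.1.2 A (cardiovascular composite and mortality) names no source.

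**Which record exists for whom.** Table 1 of the protocol has an AE row for the intervention group, up to its end-of-study visit, and none for the observational group. Its significant-medical-event row is the reverse. Section 10.14 assigns that record to low-risk participants.

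**The concern.** For a randomised patient who permanently stops tablets, two clocks run. The AE reporting clock stops 30 days after the last dose. The time-at-risk clock runs to study end. SAP 6.3.2.2 fits Cox models for active versus placebo in the intention-to-treat cohort to every secondary outcome except C, H and J, so A and B are included.

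The off-drug patient moves to the observational visit schedule, which has no AE entry. The record that schedule does use is assigned to low-risk patients. Neither document says which form carries an off-drug retinopathy or cardiovascular event in a randomised patient, or whether an event recorded elsewhere counts in an outcome collected from AEs. Sites could reasonably do different things.

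If off-drug events are lost while the time is kept, event rates for B, and for non-fatal A, are understated. If more patients stop spironolactone than placebo, the hazard ratio is pushed towards benefit. Unequal stopping is plausible: Protocol 14.1 lists hyperkalaemia and gynaecomastia among the potential common side effects, and Appendix 1 contains permanent stops for potassium.

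The high- versus low-risk comparison is also touched, because event recording in low-risk patients has no 30-day limit.

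**Working it through.** **1. Which outcomes are exposed**

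| Outcome | How the event reaches the data | Exposed off drug? |
|---|---|---|
| Primary, other UACR, eGFR, potassium (SAP 6.1.1; 6.1.2 C to I, K) | Laboratory measurement | No |
| All-cause death within A | Vital status, Protocol 14.6 | No |
| Non-fatal cardiovascular part of A | AE entry in the eCRF, 13.3.1.1; no source named in the SAP | Plausibly |
| B, retinopathy and laser | AEs only, by its stated source | Yes, if the source is applied as written |

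**2. Consistency check on the source rule.** SAP 6.3.1.2 also applies outcome B to the observational cohort, and Protocol 5.5.1 gives the same AE source for the total population. Table 1 gives low-risk patients no AE entry. Taken literally, no low-risk patient could have outcome B. The source rule therefore needs repair whatever is decided about off-drug patients.

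**3. Size of the loss in the extreme case.** The documents give no figure on this point and no rate of stopping study drug. The 129 per arm in Protocol 15.1 rests on the UACR endpoint and does not change.

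Inputs:
- Follow-up T of 104 to 230 weeks (protocol synopsis), that is 728 to 1,610 days.
- Capture ends 30 days after the last dose (13.3.2.1).
- Assumed: a proportion q stops permanently, stopping times are uniform over follow-up, and nothing is captured afterwards.

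Share of follow-up without capture: L = q × (T − 30)² / (2T²).

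- T = 728: (698/728)²/2 = 0.460, so L = 0.460q.
- T = 1,610: (1,580/1,610)²/2 = 0.482, so L = 0.482q.

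With a true ratio of 1, the apparent ratio is (1 − L active)/(1 − L placebo).

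| Stopping, active / placebo (assumed) | L active | L placebo | Apparent ratio, 104 to 230 weeks |
|---|---|---|---|
| 10% / 10% | 4.6–4.8% | 4.6–4.8% | 1.00 |
| 15% / 8% | 6.9–7.2% | 3.7–3.9% | 0.967–0.965 |
| 20% / 10% | 9.2–9.6% | 4.6–4.8% | 0.952–0.949 |
| 25% / 10% | 11.5–12.0% | 4.6–4.8% | 0.928–0.924 |
| 30% / 15% | 13.8–14.4% | 6.9–7.2% | 0.926–0.922 |
| 30% / 10% | 13.8–14.4% | 4.6–4.8% | 0.904–0.899 |

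Timing matters. If every stop came right after baseline, L = q(T − 30)/T. Then 20% versus 10% gives about 0.89, and 30% versus 10% gives 0.78 to 0.79.

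**4. Size against precision.** Assume 3% per year (not in the documents), 300 patients, and mean follow-up (2 + 4.4)/2 = 3.2 years. Expected events: 0.03 × 300 × 3.2 ≈ 29. SE(log HR) ≈ 2/√29 ≈ 0.37. A ratio of 0.97 lies |ln 0.97|/0.37 ≈ 0.08 SE from 1, 0.92 about 0.22 SE, and 0.90 about 0.28 SE.

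**The case against.** A reader might infer that AE-sourced endpoints simply cannot occur after study drug stops. The documents do not support that.

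- Protocol 14.6 orders endpoint follow-up off drug, by visits or through outside sources, with the aim of covering all included patients.
- Section 6.2 has vascular events, retinopathy status, laser treatment and secondary endpoints registered for the observational group, whose visit schedule the off-drug patient joins. Section 10.14 marks the 5.5.1 endpoints as of special interest. Section 6.3 lists secondary endpoints beside AEs for the intervention group.
- The 30-day limit stands under reporting requirements. The documentation section sets no such stop and asks for record review at each visit, and Table 1 carries AE entry to the end-of-study visit without an on-drug condition.
- Since low-risk patients have no AE form, AEs in outcome B may have been meant loosely, to include significant medical events.

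A reader might also count every potassium-related hold as lost time. A patient who restarts after a temporary hold has not yet taken the last dose, so only permanent stops close the window.

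It is also fair that A and B are secondary, that SAP 4.1 gives secondary p-values only if the primary analysis is significant, and that the possible bias is small beside the imprecision.

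All of this stands, and it turns the claim from certain loss to unassured capture. It does not close the gap. The intention in 14.6 is not tied to a form or to the definitions of A and B. The one written source for B is AEs, and the substitute record is assigned to the wrong group for these patients.

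**Conclusion.** The concern holds in limited form. AE/SAE reporting ends 30 days after the last dose, while time at risk for a randomised patient who has permanently stopped runs to study end, and the SAP does not align the two. Off-drug retinopathy and laser events, and plausibly non-fatal cardiovascular events, in the high-risk group have no assured place in outcomes B and A.

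If nothing were captured off drug and stopping were spread evenly over follow-up, a true active/placebo ratio of 1 would appear as about 0.90 to 0.97 for the unequal stopping rates tried, and would be unbiased with equal stopping, though about 5% of follow-up would lack capture at 10% stopping. Stopping concentrated just after baseline would enlarge the bias. For each assumed pattern these are upper bounds, because 14.6 provides other capture, and the stopping rates are assumptions throughout. They should not be read as the expected bias.

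In the high- versus low-risk comparison, off-drug loss would fall only on the high-risk stratum. The literal AE-only source for B would instead remove events from the low-risk stratum, so no net direction can be stated until the source is fixed.

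**What to change.** **Protocol.** Reconcile 13.3.2.1, 10.14, 14.6 and Table 1. State that the 30-day limit applies to general safety reporting. Add that cardiovascular events, retinopathy and laser treatment are recorded for every randomised patient until the final assessment, on or off study drug, and name the form (for instance, by opening the significant-medical-event record to off-drug randomised patients).

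**SAP.** In 6.1.2 A and B, take events from AEs, significant medical events and the outside sources named in Protocol 14.6. This also gives low-risk patients a valid source for B. Where a patient's endpoint information stops before study end, end time at risk for A and B at that point, with a matching exception in 6.2. Use this only as a fallback: it assumes that loss of information is unrelated to risk, which full capture does not need.

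**Cost.** About one sentence in each document and a small amount of extra data entry for off-drug patients. The visits, the form and the outside-source route already exist. The definitions of the laboratory outcomes and the sample size do not change.
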